Appendix 3.1.2. Ethical Review

The investigator or an appropriate local representative must give assurance that the ethical review board (ERB) was properly constituted and convened as required by International Conference on Harmonisation (ICH) guidelines and other applicable laws and regulations.

Documentation of ERB approval of the protocol and the ICF must be provided to Eli Lilly and Company (Lilly) before the study may begin at the investigative site(s). Lilly or its representatives must approve the ICF, including any changes made by the ERBs, before it is used at the investigative site(s). All ICFs must be compliant with the ICH guideline on good clinical practice (GCP).

The study site's ERB(s) should be provided with the following:

- the protocol and related amendments and addenda, current Investigator Brochure (IB) and updates during the course of the study
- ICF
- other relevant documents (for example, curricula vitae, advertisements)

Appendix 3.1.3. Regulatory Considerations

This study will be conducted in accordance with:

- consensus ethics principles derived from international ethics guidelines, including the Declaration of Helsinki and Council for International Organizations of Medical Sciences (CIOMS) International Ethical Guidelines
- applicable ICH GCP Guidelines
- applicable laws and regulations

Some of the obligations of the sponsor will be assigned to a third party.

Appendix 3.1.4. Investigator Information

Physicians with a specialty in endocrinology or primary care physicians specializing in endocrinology or internal medicine will participate as investigators in this clinical trial.

Appendix 3.1.5. Protocol Signatures

The sponsor's responsible medical officer will approve the protocol, confirming that, to the best of his or her knowledge, the protocol accurately describes the planned design and conduct of the study.

After reading the protocol, each principal investigator will sign the protocol signature page and send a copy of the signed page to a Lilly representative.

Appendix 3.1.6. Final Report Signature

The CSR coordinating investigator will sign the final clinical study report (CSR) for this study, indicating agreement that, to the best of his or her knowledge, the report accurately describes the conduct and results of the study.

An investigator will be selected by the Lilly study team to serve as the CSR coordinating investigator. The sponsor's responsible medical officer and statistician will approve the final CSR for this study, confirming that, to the best of his or her knowledge, the report accurately describes the conduct and results of the study.

Appendix 3.2. Data Quality Assurance

To ensure accurate, complete, and reliable data, Lilly or its representatives will do the following:

- provide instructional material to the study sites, as appropriate
- sponsor start-up training to instruct the investigators and study coordinators. This training will give instruction on the protocol, the completion of the case report forms (CRFs), and study procedures.
- make periodic visits to the study site
- be available for consultation and stay in contact with the study site personnel by mail, telephone, and/or fax
- review and evaluate CRF data and use standard computer edits to detect errors in data collection
- conduct a quality review of the database.

In addition, Lilly or its representatives will periodically check a sample of the patient data recorded against source documents at the study site. The study may be audited by Lilly or its representatives, and/or regulatory agencies at any time. Investigators will be given notice before an audit occurs.

The investigator will keep records of all original source data. This might include laboratory tests, medical records, and clinical notes. If requested, the investigator will provide the sponsor, applicable regulatory agencies, and applicable ERBs with direct access to original source documents.

Appendix 3.2.1. Data Capture System

An electronic data capture system will be used in this study. The site maintains a separate source for the data entered by the site into the sponsor-provided electronic data capture system.

Some or all of a patient's data will be directly entered into the eCRF at the time that the information is obtained. In instances where direct data entry is not used, the site will maintain source documentation in the trial files, and the patient's data will be transcribed into the eCRF. Paper documentation provided by the patient will serve as the source document, including a study drug administration log and an event-medication diary, that will be identified and documented by each site in that site's study file.

Case report form data will be encoded and stored in a clinical trial database. Data managed by a central vendor, such as laboratory test data, will be stored electronically in the central vendor's database system. Data will subsequently be transferred from the central vendor to the Lilly data warehouse.

Data from complaint forms submitted to Lilly will be encoded and stored in the global product complaint management system.

Appendix 3.3. Study and Site Closure

Appendix 3.3.1. Discontinuation of Study Sites

Study site participation may be discontinued if Lilly, the investigator, or the ERB of the study site judges it necessary for medical, safety, regulatory, or other reasons consistent with applicable laws, regulations, and GCP.

Appendix 3.3.2. Discontinuation of the Study

The study will be discontinued if Lilly judges it necessary for medical, safety, regulatory, or other reasons consistent with applicable laws, regulations, and GCP.

Appendix 3.4. Publication Policy

The publication policy for Study I8B-MC-ITSD is described in Clinical Trial Agreement.

Appendix 4. Hepatic Monitoring Tests for Treatment-Emergent Abnormality

Selected tests may be obtained in the event of a treatment-emergent hepatic abnormality and may be required in follow-up with patients in consultation with the Lilly, or its designee, clinical research physician.

Hepatic Monitoring Tests

Hepatic Hematology^a

Hemoglobin
 Hematocrit
 RBC
 WBC
 Neutrophils, segmented
 Lymphocytes
 Monocytes
 Eosinophils
 Basophils
 Platelets

Hepatic Chemistry^a

Total bilirubin
 Direct bilirubin
 Alkaline phosphatase
 ALT
 AST
 GGT
 CPK

Haptoglobin^a

Hepatic Coagulation^a

Prothrombin time
 Prothrombin time, INR

Hepatic Serologies^{a,b}

Hepatitis A antibody, total
 Hepatitis A antibody, IgM
 Hepatitis B surface antigen
 Hepatitis B surface antibody
 Hepatitis B core antibody
 Hepatitis C antibody
 Hepatitis E antibody, IgG
 Hepatitis E antibody, IgM

Anti-nuclear antibody^a

Anti-smooth muscle antibody (or anti-actin antibody)^a

Abbreviations: ALT = alanine aminotransferase; AST = aspartate aminotransferase; CPK = creatinine phosphokinase; GGT = gamma-glutamyl transferase; Ig = immunoglobulin; INR = international normalized ratio; RBC = red blood cells; WBC = white blood cells.

^a Assayed by Lilly-designated or local laboratory (if test results are required urgently to manage patient care).

^b Reflex/confirmation dependent on regulatory requirements and/or testing availability.

Appendix 5. World Health Organization Classification for Diabetes

Type 1 Diabetes Mellitus: Type 1 diabetes is judged to be present when the classical symptoms of diabetes (thirst, polyuria, wasting and stupor, or coma) are associated with readily detectable concentrations of glucose and ketone bodies in the blood and urine. Insulin treatment is necessary not only to control hyperglycemia, but also to prevent spontaneous ketosis and death (Bennett 1991; Alberti and Zimmet 1998).

Type 2 Diabetes Mellitus: Type 2 Diabetes (T2D), although often asymptomatic, may also present with classical hyperglycemic symptoms (thirst, polyuria, and weight loss), but despite hyperglycemia, ketone bodies are present in only low concentrations in the blood and urine. Coma is rare in T2D, but may result from extreme hyperglycemia and hyperosmolarity; lactic acidosis or ketoacidosis can also occur in fulminating illness (for example, severe infection or mesenteric artery thrombosis) because of acute increase in insulin requirements, but spontaneous ketosis does not occur. Some patients with T2D later progress to a state of absolute insulin deficiency (Bennett 1991; Alberti and Zimmet 1998).

References:

- Bennett P. Classification and diagnosis of diabetes mellitus and impaired glucose tolerance. In: Pickup JC, Williams G, editors. *Textbook of diabetes*. Vol. 1. 1st ed. Oxford: Blackwell Scientific Publications; 1991:p 37-44.

Appendix 6. New York Heart Association Cardiac Disease Classification

Functional Capacity

Class I

Patients with cardiac disease but without resulting limitation of physical activity. Ordinary physical activity does not cause undue fatigue, palpitation, dyspnea, or anginal pain.

Class II

Patients with cardiac disease resulting in slight limitation of physical activity. They are comfortable at rest. Ordinary physical activity results in fatigue, palpitation, dyspnea, or anginal pain.

Class III

Patients with cardiac disease resulting in marked limitation of physical activity. They are comfortable at rest. Less than ordinary activity causes fatigue, palpitation, dyspnea, or anginal pain.

Class IV

Patients with cardiac disease resulting in inability to carry on any physical activity without discomfort. Symptoms of heart failure or the anginal syndrome may be present even at rest. If any physical activity is undertaken, discomfort increases.

1994 Revisions to Classification of Functional Capacity and Objective Assessment of Patients with Diseases of the Heart

www.americanheart.org. ©2011, American Heart Association, Inc.

### 3. Revision History

Statistical analysis Plan (SAP) Version 1 was approved prior to the first patient visit. Version 1 was based on the Protocol I8B-FH-ITSE (ITSE) approved on 27 June 2018.

The main changes of SAP Version 2 are listed below.

- Analysis period of from randomization to Week 26 (including all data regardless of IP use) was added for some of the safety analysis.
- Removed the baseline rate covariate from all hypoglycemia models as there were many critical outliers leading to inaccurate in the LSM and the biases were inconsistent.
- For adjustments of covariates, HbA1c stratum at Visit 7 is changed to HbA1c stratum at baseline to be consistent with the global study ITRN..
- COVID-19 related analyses are added.
- Weights of the graphical testing scheme for the multiple testing of this study are updated by simulation and team decision.

## 4. Study Objectives

Table 4.1 shows the objectives and endpoints of the study.

**Table 4.1. Objectives and Endpoints**

Objectives	Endpoints
Primary Objective	

 
To test the hypothesis that LY900014 is noninferior to insulin lispro on glycemic control (NIM=0.4% for HbA1c) in patients with T2D, when administered as prandial insulin (0 to 2 minutes prior to the meal), in combination with basal insulin glargine or insulin degludec for 26 weeks
 
	
 
Difference between LY900014 and insulin lispro in change from baseline to Week 26 in HbA1c
 

Multiplicity-Adjusted Objectives	

 
To test the hypothesis that LY900014 is superior to insulin lispro in controlling 1-hour PPG excursions, when administered as prandial insulin
 
	
 
Difference between LY900014 and insulin lispro in the 1-hour PPG excursion (serum glucose measured 1 hour after the start of the meal minus fasting serum glucose) from an MMTT at Week 26
 

 
To test the hypothesis that LY900014 is superior to insulin lispro in controlling 2-hour PPG excursions when administered as prandial insulin
 
	
 
Difference between LY900014 and insulin lispro in the 2-hour PPG excursion (serum glucose measured 2 hours after the start of the meal minus fasting serum glucose) from an MMTT at Week 26
 

 
To test the hypothesis that LY900014 is superior to insulin lispro on improving glycemic control (HbA1c) when administered as prandial insulin
 
	
 
Difference between LY900014 and insulin lispro in change from baseline to Week 26 in HbA1c
 

Other Secondary Objectives	

 
To compare LY900014 and insulin lispro with respect to the rate of severe hypoglycemic events
 
	
 
Rate (events/patient/100 years) of severe hypoglycemic events from baseline through Week 26
 


 
To compare LY900014 and insulin lispro with respect to the incidence and rate of documented symptomatic postmeal hypoglycemia
 
	
 
Rate (events/patient/year and/or events/patient/30 days) and incidence (percent of patients with at least 1 event) of documented symptomatic postmeal hypoglycemia within 1 and 2 hours after start of a meal from baseline through Week 26
 

 
To compare LY900014 and insulin lispro with respect to the incidence and rate of documented symptomatic hypoglycemia
 
	
 
Rate (events/patient/year and/or events/patient/30 days) and incidence (percent of patients with at least 1 event) of documented symptomatic hypoglycemic events from baseline through Week 26
 

 
To compare LY900014 and insulin lispro with respect to 1,5-AG
 
	
 
Change from baseline in 1,5-AG values at Week 26
 

 
To compare LY900014 and insulin lispro with respect to 10-point SMBG profiles
 
	
 
Change from baseline in 10-point SMBG values at Week 26
 

 
To compare LY900014 and insulin lispro with respect to total, basal, and prandial insulin dose
 
	
 
Change from baseline in total, basal and prandial insulin dose and prandial/total insulin dose ratio at Week 26
 

--	---

**Objectives and Endpoints**

Objectives	Endpoints
Other Secondary Objectives (Continued)	

 
To compare LY900014 and insulin lispro with respect to the proportion of patients achieving HbA1c targets
 
	
 
The proportion of patients with HbA1c <7% and ≤6.5% at Week 26
 

Tertiary/Exploratory Objectives	

 
To compare the safety of LY900014 relative to insulin lispro
 
	
 
Adverse events, vital signs, chemistry, and hematology laboratory measures
 

 
To compare the incidence of treatment-emergent anti-insulin lispro antibodies for LY900014 and insulin lispro
 
	
 
Incidence of treatment-emergent positive anti-insulin lispro antibodies
 

 
To compare LY900014 and insulin lispro with respect to quality of life as measured by the EQ-5D-5L
 
	
 
Change from baseline in EQ-5D-5L UK-population based health state index score and EQ-VAS score at Week 26
 

 
To compare LY900014 and insulin lispro with respect to diabetes treatment satisfaction as measured by the ITSQ
 
	
 
Change from baseline in ITSQ regimen inconvenience and lifestyle flexibility domain scores at Week 26
 

 
To compare LY900014 and insulin lispro with respect to the impact that diabetes has on the ability to work and perform regular activities as measured by the WPAI-GH
 
	
 
Change from baseline in WPAI-GH item scores at Week 26
 

 
To compare LY900014 and insulin lispro with respect to changes in body weight
 
	
 
Change from baseline to Week 26 in weight (kg)
 

 
To compare LY900014 and insulin lispro with respect to glycemic variability
 
	
 
Within-day and between-day glycemic variability measured by the standard deviation and the coefficient of variation of 10-point SMBG profiles
 

Abbreviations: 1,5-AG = 1,5-Anhydroglucitol; EQ-5D-5L = European Quality of Life – 5 Dimensions 5 Level; EQ-VAS = EuroQol visual analog scale; HbA1c = hemoglobin A1c; ITSQ = Insulin Treatment Satisfaction Questionnaire; MMTT = mixed-meal tolerance test; NIM = non-inferiority margin; PPG = postprandial glucose; SMBG = self-monitored blood glucose; T2D = type 2 diabetes; WPAI-GH = Work Productivity and Activity Impairment Questionnaire General Health.

## 5. Study Design

### 5.1. Summary of Study Design

Study I8B-FH-ITSE (ITSE) is a Phase 3, prospective, double-blind, randomized, multinational, multicenter, 2-group, parallel, active-controlled study conducted in patients with type 2 diabetes mellitus (T2D) currently treated with basal insulin in combination with at least 1 prandial insulin injection OR premixed insulin with at least 2 injections daily. Patients will be randomized to 1 of the 2 treatment groups in 2:1 ratio (LY900014: insulin lispro). Each of the treatment therapies, LY900014 and insulin lispro, will be administered immediately (0-2 minutes) prior to each meal in a double-blind manner. The study is designed to demonstrate noninferiority of LY900014 when compared with insulin lispro in change from baseline to Week 26 in HbA1c, when both are administered at the start of the meal. The study includes a 1-week screening period and an 8-week lead-in period, followed by a 26-week treatment period, and a 4-week safety follow-up period. **Abbreviations:** T = telephone visit; wk = week.

- a At Visit 2, patients treated with insulin aspart, insulin glulisine, regular insulin, or premixed insulin will be transferred to insulin lispro. At Visit 2, patients treated with a basal insulin regimen other than insulin glargine U-100 or insulin degludec will be transferred to insulin glargine U-100 once daily or insulin degludec U-100 once daily. At Visit 8, patients will be randomized to either insulin lispro or LY900014 and continue their basal insulin regimen.
- b Titrate basal insulin.
- c Titrate prandial insulin (insulin lispro or LY900014).
- d Patients will discontinue study insulins at Week 26.

[figure not shown]
Figure 5.1 illustrates the study design.

### 5.2. Determination of Sample Size

Patients will be randomized in a 2:1 ratio to LY900014 and insulin lispro, both administered 0 to 2 minutes before meals. Assuming a non-inferiority margin (NIM) of 0.4%, no true difference between treatment arms, and an SD of 1.1%, 480 completers (320 in the LY900014 group and 160 in the insulin lispro group) will provide 96% power to show noninferiority between LY900014 and insulin lispro using the upper limit of a 2-sided 95% confidence interval (CI; LY900014 – insulin lispro). Assuming a 15% dropout rate for 26 weeks, approximately 564 patients will need to be randomized.

### 5.3. Method of Assignment to Treatment

Patients who meet all criteria for enrollment will be randomized to double-blind treatment at Visit 8. Assignment to treatment groups will be determined by a computer-generated random sequence using an interactive web-response system (IWRS). Patients will be randomized to 1 of the 2 treatment groups in 2:1 ratio (double-blind LY900014 administered at meal time:double-blind insulin lispro administered at meal time). Stratification will be by country (China vs. Other), HbA1c stratum at Visit 7 ( $\leq 8.5\%$  vs.  $> 8.5\%$ ), and type of basal insulin during the lead-in period (glargine U-100 vs. degludec U-100), and number of prandial doses at study entry ( $< 3$  vs.  $\geq 3$ ).

Abbreviations: T = telephone visit; wk = week.

- a At Visit 2, patients treated with insulin aspart, insulin glulisine, regular insulin, or premixed insulin will be transferred to insulin lispro. At Visit 2, patients treated with a basal insulin regimen other than insulin glargine U-100 or insulin degludec will be transferred to insulin glargine U-100 once daily or insulin degludec U-100 once daily. At Visit 8, patients will be randomized to either insulin lispro or LY900014 and continue their basal insulin regimen.
- b Titrate basal insulin.
- c Titrate prandial insulin (insulin lispro or LY900014).
- d Patients will discontinue study insulins at Week 26.

**Figure 5.1. Illustration of study design.**

## 6. A Priori Statistical Methods

### 6.1. General Considerations

Statistical analysis of this study will be the responsibility of Eli Lilly and Company (hereafter Lilly). Any change to the data analysis methods described in the protocol will require an amendment ONLY if it changes a principal feature of the protocol. Any other change to the data analysis methods described in the protocol, and the justification for making the change, will be described in this SAP and/or in the clinical study report (CSR). Additional exploratory analyses will be conducted, as deemed appropriate.

For purposes of analysis, the following populations are defined in [Table 6.1](#):

**Table 6.1. Patient Populations**

Population	Description
Entered	All patients who give informed consent.
Enrolled	All patients who receive at least 1 dose of open-label insulin lispro in the 8-week lead-in period.
Randomized	All patients who are randomly assigned to study treatment at Visit 8. Treatment group will be defined on the basis of the treatment the patients are assigned.
Safety	All randomized patients who receive at least 1 dose of the randomly assigned investigational product (IP). Treatment group will be defined on the basis of the treatment the patients are assigned.
Completer	Patients included in the randomized population who have completed Week 26 of study treatment without permanent discontinuation of IP. Treatment group will be defined on the basis of the treatment the patients are assigned.
Per Protocol	Patients included in the randomized population who have completed Week 26 of study treatment without permanent discontinuation of IP and without significant protocol deviations through Week 26 that would significantly impact the primary objective. Treatment group will be defined on the basis of the treatment the patients actually receive.

Unless otherwise stated, the efficacy analyses will be conducted on the Randomized Population, and the safety analyses will be conducted on the Safety Population.

The primary analysis is for the treatment period through Week 26.

Unless otherwise noted, all tests of treatment effects will be conducted at a 2-sided alpha level of 0.05, and CIs will be calculated at 95%, 2-sided. All tests of interactions between treatment groups and other factors will be conducted at a 2-sided alpha level of 0.10.

The definitions of baseline and post-baseline for the efficacy and safety analyses depend on which analysis period is being used. The following analysis periods will be used:

- Lead-in Period – Visits 2 to 8
- 26-Week Treatment Period – from randomization to Week 26 prior to discontinuation of investigational product (IP)
- 
- 26-Week Treatment Period and Safety Follow-Up Visit – from randomization to Visit 801 (including all data regardless of IP use)

The data on IP is defined based on the following rules:

- For data only measured at an office visit
  - Mixed-meal tolerance test (MMTT) postbaseline data will be classified as on IP if the MMTT performance date is prior to or on the last IP dose date
  - Other postbaseline data (for example, vital signs, safety laboratory tests, and questionnaires) will be considered as on IP if the measurement was performed at or prior to the cutoff date defined as 14 days after the last IP dose date
- For data collected as running records with an exact date stamp such as adverse events (AEs) and diary entries where the dates of the measures were not tied with the date of an office visit, postbaseline data with dates  $\leq$  (last study drug dose date +1) will be considered as data on IP.

Table 6.2 describes the rules for determining the patient population, baseline and postbaseline observations for the different analysis periods.

For continuous measures, summary statistics will include sample size, mean, SD, median, minimum, and maximum for both the actual and the change from baseline measurements. Least-squares (LS) means and standard errors derived from the analysis models will also be displayed. Treatment comparisons will be displayed showing the treatment difference LS means and the 95% CIs for the treatment differences, along with the p-values for the treatment comparisons.

For categorical measures, summary statistics will include sample size, frequency, and percentages. Fisher's exact test will be used for treatment comparisons.

For laboratory values, Systeme International (SI) units will be presented. Both % and mmol/mol will be presented for HbA1c and mmol/L will be presented for glucose measurements.

All baseline measures will be analyzed using an analysis of variance (ANOVA) model that has treatment as the model term.

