7.2. Method of Treatment Assignment

Patients who meet all criteria for enrollment will be randomized to double-blind treatment at Visit 8. Assignment to treatment groups will be determined by a computer-generated random sequence using an interactive web-response system (IWRS). Patients will be randomized to 1 of the 2 treatment groups in 2:1 ratio (double-blind LY900014 administered at meal time:double-blind insulin lispro administered at meal time). Stratification will be by country (China vs. Other), HbA1c stratum ($\leq 8.5\%$ vs. $> 8.5\%$ at Visit 7), and type of basal insulin during the lead-in period (glargine U-100 vs. degludec U-100), and number of prandial doses at study entry (< 3 vs. ≥ 3).

The IWRS will be used to assign all IP during the study, including insulin lispro during the lead-in period. The IWRS will be used to assign prefilled pens containing double-blind IP to each patient randomized to the 2 blinded study groups. Site personnel will confirm that they have located the correct prefilled pens by entering a confirmation number found on the prefilled pen into the IWRS.

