10.2. Populations for Analyses

For purposes of analysis, the following populations are defined:

Population	Description
Entered	All patients who sign informed consent.
Enrolled	All patients who receive at least 1 dose of open-label insulin lispro in the 8-week lead-in period.
Randomized	All patients who are randomly assigned to study treatment at Visit 8. Treatment group will be defined on the basis of the treatment the patients are assigned.
Safety	All randomized patients who receive at least 1 dose of the randomly assigned IP.
Completer	Patients included in the randomized population who have completed Week 26 of study treatment without permanent discontinuation of IP.
Per Protocol	Patients included in the randomized population who have completed Week 26 of study treatment without permanent discontinuation of IP and without significant protocol deviations through Week 26 that would significantly impact the primary objective. Treatment group will be defined on the basis of the treatment the patients actually receive.

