### 6.12.3. Deaths

The listing of all deaths by patient for all enrolled patients will be provided as part of the SAE listing, regardless of the investigator's or the sponsor's judgment about causality. Each listing will include study ID, investigator ID, patient ID, treatment group, baseline age, sex, associated AE, first and last dose date for open label insulin lispro and randomized IP, and the event date.

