### 7.5. Some Mitigation Procedures

Some mitigation procedures are conducted to reduce the impact of COVID-19 during the study, which include direct to patient drug supply, IP (bolus insulin) local purchase and Visit 7 and Visit 8 combined.

Summary and listing of IP local purchase due to the COVID-19 pandemic will be provided. Randomized participants with Visit 7 and Visit 8 combined due to the COVID-19 pandemic will be summarized by treatment.

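### Safety is defined and grouped by assigned product, so a patient who took only the other blinded insulin is excluded or counted under an insulin never taken

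*SAP*

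**What the plan says.** SAP Table 6.1 gives the Safety population two rules. Entry: "All randomized patients who receive at least 1 dose of the randomly assigned investigational product (IP". Grouping: "Treatment group will be defined on the basis of the treatment the patients are assigned". Unless otherwise stated, "the safety analyses will be conducted on the Safety Population", and SAP Table 6.2 applies it to treatment-emergent adverse events, safety laboratory tests, hypoglycemia, weight and vital signs, and anti-insulin lispro antibodies.

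Protocol 10.2 has the same entry rule, "All randomized patients who receive at least 1 dose of the randomly assigned IP", but its Safety row contains no grouping rule. The SAP supplied one without giving a reason.

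For the Per Protocol population, the same SAP table says: "Treatment group will be defined on the basis of the treatment the patients actually receive". Protocol 10.2 agrees.

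Three other places bear on the point:

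- **Dispensing control**, protocol 7.2: "Site personnel will confirm that they have located the correct prefilled pens by entering a confirmation number found on the prefilled pen into the IWRS".
- **Reporting that does not depend on the Safety population.** SAP 6.12.3: "The listing of all deaths by patient for all enrolled patients will be provided as part of the SAE listing". SAP 6.12.2 also plans a listing of all serious adverse events, and SAP 6.12.8 plans narratives for deaths, serious adverse events and discontinuations due to adverse events.
- **COVID-19 supply measures**, SAP 7.5: "direct to patient drug supply, IP (bolus insulin) local purchase and Visit 7 and Visit 8 combined".

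**The concern.** The Per Protocol row shows that the plan allows for a difference between treatment assigned and treatment received. It uses the treatment received only in a sensitivity set for efficacy. In the safety set, where it matters most which product a patient took, the plan refers to assignment twice: once for entry and once for grouping.

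The combination is a hybrid. A pure analysis by assignment would keep a wrongly supplied patient in the assigned arm. An analysis by treatment received would move the patient to the other arm. The rule as written can do a third thing, which is to remove an exposed patient altogether.

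What is at stake is the attribution of sparse events, such as hypersensitivity, injection site reactions and severe hypoglycemia. LY900014 is the new formulation. Both insulins come in blinded 100 U/mL prefilled pens, so neither patient nor site would readily notice a mix-up.

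**Working it through.** **1. The plan's own figures.** SAP 5.2 gives a margin of 0.4%, SD 1.1%, 320 and 160 completers, a 2-sided 95% interval and 15% dropout.

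- Standard error = 1.1 × √(1/320 + 1/160) = 0.1065.
- Power = Φ(0.4/0.1065 − 1.96) = Φ(1.796) = 0.964, against the stated 96%.
- Number to randomize = 480/0.85 = 564.7, against about 564.

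Both reproduce. Neither depends on the Safety population, because the primary analysis uses all randomized patients by assignment.

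**2. The two Safety rules, case by case.**

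| Patient took | Entry phrase read literally | Entry phrase read as any blinded product |
|---|---|---|
| Only the other insulin | Excluded from Safety tables | Included, counted under an insulin never taken |
| Both insulins | Included, all events under assigned arm | Same |

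**3. One misplaced patient.** 564 split 2:1 gives 376 and 188. With denominators held fixed, one patient with an event moves incidence by 1/188 = 0.53 points (insulin lispro) or 1/376 = 0.27 points (LY900014).

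**4. Dilution when mismatched patients are grouped by assignment.** Let k_L LY900014-assigned and k_C lispro-assigned patients take the wrong product throughout. The observed risk difference is then the true one multiplied by 1 − k_L/376 − k_C/188. The counts below are assumptions, since the documents give no error rate.

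| k_L, k_C | Share kept | True 5.0-point difference becomes (10% against 5%, assumed) | Safety N if excluded instead |
|---|---|---|---|
| 1, 1 | 99.2% | 4.96 | 375 and 187 |
| 4, 2 | 97.9% | 4.89 | 372 and 186 |
| 19, 9 (about 5%) | 90.2% | 4.51 | 357 and 179 |

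Exclusion does not dilute the difference in this way. It takes misclassified patients out and loses their exposure and events.

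**5. Direction of the exposure count.** Assume the same error rate in both arms, for example 1%. Then 3.76 LY900014-assigned patients take insulin lispro and 1.88 lispro-assigned patients take LY900014. Grouping by assignment counts 376 patients as exposed to LY900014, when 376 − 3.76 + 1.88 = 374.12 took it. That slightly over-counts LY900014 exposure. Under exclusion, the patients lost include 1.88 who took LY900014 and 3.76 who took insulin lispro.

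**The case against.** **The entry phrase may be innocent.** Protocol 7.2 treats lead-in insulin lispro as investigational product too, and SAP Table 6.2 separates randomized product from open-label insulin lispro. The words may only mark that boundary, in which case nobody is excluded. This is a fair reading, but it leads to the other outcome: the patient stays in and is counted under an insulin never taken.

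**Exclusion would be very rare.** Blinded product is dispensed at Visits 8, 11, 13, 15, 16 and 17. To be excluded, a patient must never take one dose of the assigned product. That needs an error at every dispensing received, or one error followed by early stopping, despite pen confirmation. This stands. The COVID-19 supply measures could be a further route to a mismatch, but the SAP does not say which product was bought locally or in which period.

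**Grouping by assignment is a deliberate choice.** It keeps the randomized comparison, and Per Protocol serves a different purpose. This is true of the grouping rule. It does not justify an entry rule that can remove an exposed patient.

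**Little would go unreported.** Deaths and serious adverse events are listed regardless, and severe hypoglycemia must be reported as serious. This stands: exclusion means exclusion from the Safety-population summaries and tests. A listing of important deviations is also planned in SAP 6.9, but that section is partly redacted, so whether it covers wrong-product cases cannot be seen. It would not change Table 6.1.

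**Two stronger readings are tempting.** A reader might infer that exposure to LY900014 is under-reported. The documents do not support this: the direction depends on how the entry rule is read and on unknown error rates, and with 2:1 allocation and equal rates, grouping by assignment over-counts it. A reader might also infer that both outcomes pull the comparison toward no difference. Only misattribution does so; exclusion does not by itself.

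**Conclusion.** The point holds as a small defect in a stated rule. On either reading of the entry phrase, a patient who took only the other blinded insulin is handled wrongly for a safety analysis, and no readable passage corrects it.

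The size is probably very small. If no mis-dispensing occurs, nothing changes. If 0.5% to 2% of 564 patients had any supply error (an assumption), that would be about 3 to 11 patients; those who never took the assigned product would be fewer still. Misattribution of a few patients would dilute a true difference by about 1% to 2% of its value, as in the first two rows of the dilution table. Individual sparse events would shift incidence by 0.27 or 0.53 points each. The trial's efficacy conclusions are not affected. It is a cheap improvement, best made before unblinding so that nobody has to decide afterwards which insulin an event belongs to.

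**What to change.** In SAP Table 6.1, with a matching line in protocol 10.2:

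- Define Safety as all randomized patients who take at least 1 dose of either blinded study insulin.
- Group patients who took only one product by the product actually received.
- Keep patients who took both products in their assigned group. Moving all of them to LY900014 would shift events that began on insulin lispro to the wrong product, which is the same fault in the other direction.
- List every mismatch, with dates and with events by the product in use at onset.

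The cost is one definition, one protocol line and one listing. Protocol 10.3.1 lets the SAP carry changes to analysis methods that do not alter a principal feature of the protocol. The downside is that safety denominators may differ from the randomized counts by a few patients, and those few leave the strictly randomized comparison.
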